#### INTRODUCTION

#### Background

After completion of 5 years of medical school training, the next step of becoming a House Officer (HO) is said to be associated with high levels of stress. It has been associated with mental health problems amongst HOs and sometimes quitting the medical line altogether. In Malaysia, the number of HOs not completing housemanship training within the allocated time is slowly declining from 86.4% (2009) to 58.8% (2012) (Lim, 2017). The dropout rate is said to be increasing yearly. This causes a lot of constraints on the HO, their family, sponsors, patients and also the country. Amongst the reason for stress is the feeling of incompetency or "fear of making mistakes". Other work-related issues include workload, time management, financial, colleague and superior related issues. Medicorp is a company that specializes in training for junior doctors and has come up with a module to help medical graduates cope with these issues. The module is a 3-day-course named the HO Preparatory Course. It was initially the brainchild of the Islamic Medical Association of Malaysia (IMAM) but was later privatized to accommodate the demand and the running of the module and courses. The module has been re-evaluated through feedback of participants and trainers to cater to the needs and wants of the newly graduate; be it local or overseas. Therefore, we would like to assess whether this intervention module is effective in addressing HO stress, consequently reducing the risk of drop out and extension in HO training

#### **Problem Statement**

Housemanship is the first 2 years of a Malaysian doctor's career. It is associated with various causes of psychological stress (Vivekanandan et al., 2016; Yusoff, Tan, & Esa, 2011) . The top cause of stressors found among House Officers (HO) is fear of making mistakes (Al-Dubai, Ganasegeran, Perianayagam, & Rampal, 2013; Yusoff et al., 2011). Time management-workload pressure, work colleague and financial issues are the other top causes of stress. (Al-Dubai et al., 2013; Yusoff et al., 2011). A more recent study suggests poor work-social life balance as a major cause of stress amongst housemen (Vivekanandan et al., 2016).

According to a recent report by the Penang Institute; a think-tank funded by the Penang state government, the percentage of HOs completing their training in Malaysia within the allocated time of 2 years has declined from 86.4% in 2009 to only 58.8% in 2012 (Lim, 2017; Penang Institute, 2018). The dropout rate, which is defined as HOs not completing their training within 5 years is said to be slowly increasing from 3.7-4.8% per batch year (Lim, 2017). In 2016 1.2% were either terminated or quit due to the inability to cope with stress (Lim, 2017).

The House Officer's Preparatory Course was initially organized by the Islamic Medical Association of Malaysia (IMAM) in early 2011 to address the mentioned issues. Since then, it has evolved and has been privatized to Medicorp, a company that specializes in junior doctor training. The module has been further refined through feedback from participants, speakers and organisers who still remain to be active IMAM members, some of them UPM lecturers. There is one main HO Peparatory Course, and also small follow up courses that covers other topics in depth.

Medicorp takes into account that peer training is one of the top learning methods preferred by junior doctors (Wiggins, Haldar, & Biswas, 2013). Hence this training course relies heavily on volunteers mainly feedback from participants and its alumni. To date there has been more than 20 courses with more than 1500 participants who have benefited from this course. The courses are now run in 3 different states based on demand, Selangor, Sabah and Kelantan. They are followed up even after the course via social media networks and whatsapp groups for further support.

Housemanship preparatory course training is slowly gaining attention here in Malaysia. Prior to this it was very limited. The modules in the training sessions vary with irregular times Research done on these training modules are also very limited if not done at all.

#### **Significance of Study**

We aim to evaluate this peer-lead course to see its effect on medical graduates' confidence, *readiness*, and psychological wellbeing to better prepare them for housemanship training. With the improvement of these factors it is hoped that this will reduce the level of stress amongst the junior doctors' just starting work to give them a head start to become a more *prepared*, confident and motivated doctor and will hopefully reduce rates of extension and dropouts.

## **Objectives**

## General

To determine the effectiveness of Medicorp's House Officer (HO) Preparatory Course for medical graduates in confidence, readiness, and psychological well-being to work as a HO.

## Specific

- To determine the socio-demographic and past clinical experience of participants attending Medicorp's HO Preparatory Course
- 2. To determine the level of confidence, readiness, and psychological well-being of participants to work as a HO before attending the Medicorp HO Preparatory course
- 3. To determine the level of confidence and readiness of participants to work as a HO after immediately attending the Medicorp HO Preparatory course
- 4. To determine the level of confidence, readiness and psychological well-being of participants to work after 1 month working as a HO
- To determine the effectiveness of the Medicorp HO Preparatory course on the level of confidence, readiness and psychological well-being before attending the course and after 1 month working as a HO
- 6. To determine the determine the effectiveness of the Medicorp HO Preparatory course on the level of confidence and readiness immediately after attending the course

## **Study Hypothesis**

- The HO Preparatory Course is an effective module in improving the confidence level, readiness and psychological well-being of participants in preparing them for HO-ship in Malaysia
- 2. The level of confidence, readiness, and psychological well-being of participants to work as a HO before attending the Medicorp HO Preparatory course is low
- 3. There is a high level of confidence and readiness of participants to work as a HO after attending the Medicorp HO Preparatory
- 4. There is a high level of confidence, readiness and psychological well-being of participants to work after 1 month working as a HO

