### Study outcome measures:

### 1. Primary outcome

a. Level of confidence:

This will be adapted from the IMU Student Competency Survey (Appendix 2) as there are no published studies on the confidence level of medical graduates before beginning HO-ship. The questionnaire comprises of 5 sections. The first 4 sections asses on generic skills, practical tasks, soft skills and their confidence as a whole, using a Likert scale assessment. Scoring is a mean score of 1-5 and the higher the score, the higher the confidence. The last section asks on the one daunting aspect of being a HO out of a list of 7 things, this section is descriptive.

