#### 2. Secondary outcome

a. Readiness

This is also adapted from the IMU competency survey and is asked on a likert scale of 1 to 5 for their level of readiness. It is assessed after the confidence section. The higher the score, the higher the level of readiness.

b. Psychological wellbeing

This is using the Depression Anxiety Stress Scale (DASS): This questionnaire is used to asses Depression, Anxiety and Stress. It uses a likert scale. The scores indicate normal, mild, moderate, severe and extremely severe for each of the domains. The higher the scores, indicates the more severe the conditions.

Each of the three DASS-21 scales contains 7 items, divided into subscales with similar content. The depression scale assesses dysphoria, hopelessness, devaluation of life, self-deprecation, lack of interest / involvement, anhedonia and inertia. The anxiety scale assesses autonomic arousal, skeletal muscle effects, situational anxiety, and subjective experience of anxious affect. The stress scale is sensitive to levels of chronic non-specific arousal. It assesses difficulty relaxing, nervous arousal, and being easily upset / agitated, irritable / over-reactive and impatient. Scores for depression, anxiety and stress are calculated by summing the scores for the relevant items.

The DASS-21 is based on a dimensional rather than a categorical conception of psychological disorder. The assumption on which the DASS-21 development was based (and which was confirmed by the research data) is that the differences between the depression, anxiety and the stress experienced by normal subjects and clinical populations are essentially differences of degree. The DASS-21 therefore has no direct implications for the allocation of patients to discrete diagnostic categories postulated in classificatory systems such as the DSM and ICD. (Lovibond & Lovibond, 1995)

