### Sample size

Sample size was calculated using G\*Power 3.1 sample size calculator software. Based on reports by confidence score from a study analysing pre and post emergency department posting in junior doctors was used. The mean overall confidence score was 56.475(24.67) at the end of month 1 and 62.775(28.69) at the end of month 4(Williams et al., 1997). The estimated sample size was 208 participants after accounting for power of 80%, significance level of 0.05% and 30% attrition.

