#### **Data Analysis**

The data will be analysed using IBM Social Package for Social Science (SPSS) version 24. A descriptive analysis of the demographic characteristics of the participants, clinical experience and baseline level of confidence, readiness and psychological wellbeing will be reported using means and standard deviations (SD) or median and inter-quartile range (IQR) for continuous variables (depending on the data distribution) and as frequencies and percentages for categorical data. An analysis to compare between participants who completed and withdrew from the study will be made using Chi-square or Exact test (for unbalanced data) for categorical variables and independent t-test for continuous data.

A repeated measures ANOVA will be conducted to determine the effectiveness of the intervention within the groups across the study periods (baseline, immediately after intervention and at 1 month after working). Controlling for baseline measures will be done to determine the change over time on the measured outcomes (level of confidence, readiness and psychological wellbeing). All analyses conducted are two-tailed with significant level set at p value <0.05.

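### Hypothesis 1 makes one effectiveness claim over three domains, but only confidence is primary and powered, and no rule says which results would support the claim.

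*Combined protocol and SAP*

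**What the plan says.** - **Claim.** Hypothesis 1 (Study Hypothesis) reads "The HO Preparatory Course is an effective module in improving the confidence level, readiness and psychological well-being of participants". The general objective likewise concerns effectiveness "in confidence, readiness, and psychological well-being to work as a HO". The specific objective comparing before the course with 1 month as a house officer also names all three domains.
- **Hierarchy.** Under Study outcome measures, the primary outcome has one entry, "a. Level of confidence". Readiness and psychological well-being come under "2. Secondary outcome".
- **Well-being.** This is measured with the DASS, which yields three scores: "Scores for depression, anxiety and stress are calculated by summing the scores for the relevant items". No rule combines them into one statement about well-being.
- **Sample size.** The basis is confidence only: "Based on reports by confidence score from a study analysing pre and post emergency department posting in junior doctors was used". The figures used are "The mean overall confidence score was 56.475(24.67) at the end of month 1 and 62.775(28.69) at the end of month 4".
- **Testing.** The Data Analysis section plans a repeated measures ANOVA over the study periods and adds: "All analyses conducted are two-tailed with significant level set at p value <0.05". It gives no testing order, no multiplicity adjustment and no condition under which hypothesis 1 counts as supported.
- **Timing.** Under Study Design, confidence and readiness are measured at all three time points. The DASS is not measured immediately after the course.

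**The concern.** The outcome section ranks the domains, but the hypothesis and objectives treat them as equals and the analysis section never uses the ranking. The stated power and significance level therefore belong to one comparison, while the conclusion the study wants to draw covers three.

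Because no decision rule is written down, it can be chosen after the results are known. Nothing in the plan prevents a significant readiness result, or one DASS scale, from carrying the statement that the module is effective while confidence, the primary outcome, shows nothing. Conversely, if the hypothesis is held to its wording and all three must improve, the study may fail to support it more often than 80% power suggests.

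**Working it through.** **1. The plan's own figure, for confidence alone.** Inputs from the Sample size section are means 56.475 and 62.775, SDs 24.67 and 28.69, power 80% and attrition 30%. Alpha is taken as 0.05 two-sided, as in the Data Analysis section. The Sample size section prints 0.05%, but reading that literally as 0.0005 gives 496, so 208 fits only 0.05. The pre-post correlation r is not given; r = 0.5 is assumed because it reproduces the stated number.

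- Difference: 62.775 − 56.475 = 6.3.
- SD of the difference: √(24.67² + 28.69² − 2 × 0.5 × 24.67 × 28.69) = 26.906.
- Standardised effect: 6.3 / 26.906 = 0.234.
- Paired t-test power (noncentral t): 79.97% with 145 completers, 80.2% with 146.
- Inflated for attrition: 145 / 0.70 = 207.1, so 208; 146 / 0.70 = 208.6, so 209.

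The stated 208 is therefore the size for one confidence comparison.

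**2. Set-up for the three-domain claim.** The documents give no effect size for readiness or DASS and no correlation between outcomes. Assumptions: each domain alone has 80% power, and the correlation ρ between test statistics is the same for each pair. With critical value 1.96, the noncentrality is 1.96 + 0.84 = 2.80. Under independence, power for all three is 0.8³, power for at least one is 1 − 0.2³, and the chance of at least one false significance is 1 − 0.95³. For ρ > 0 the multivariate normal distribution is used.

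| ρ | Power, all three required | Power, any one suffices | Chance of at least one false two-sided significance (three tests) |
|---|---|---|---|
| 0 | 51% | 99% | 14.3% |
| 0.3 | 57% | 97% | 13.6% |
| 0.5 | 61% | 95% | 12.5% |
| 0.7 | 66% | 92% | 10.9% |

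**3. Which property fails under which rule.**

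- *All three required.* A false claim needs a false significance in at least one domain with no effect, together with significance in the others. Its probability cannot exceed that of a single 0.05 test (intersection-union principle). Error is at most 5%; only power falls.
- *Any one suffices.* Power is at least that of confidence alone; only error rises. Counting only favourable results, it is 7.3% at ρ = 0, 6.3% at 0.5 and 5.5% at 0.7, against 2.5% for a single test.

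**4. DASS counted as three scales (five tests).** Under independence, power for all five is 0.8⁵ = 33%, and the chance of at least one false significance is 1 − 0.95⁵ = 22.6%. There is a side case: if all three domains are required but well-being counts as improved on any one DASS scale, error on that component alone can reach 1 − 0.95³ = 14.3%.

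**5. Cost of the alternatives, at standardised effect 0.234 for every domain.** Requiring all three with 80% joint power under independence needs 0.8^(1/3) = 92.8% power per domain: 216 completers, or 216 / 0.70 = 309 enrolled. A Bonferroni level of 0.05/3 needs 194 completers, or 194 / 0.70 = 278 enrolled. At 145 completers, power per outcome at that level is 65%.

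**The case against.** The strongest reply is that the hierarchy already exists. Confidence is named primary, readiness and DASS are secondary, and the sample size follows the primary. One unadjusted primary outcome with supportive secondaries is a common structure, and its 5% and 80% were only ever meant for the primary. The Study Hypothesis list is also partly descriptive, expecting low or high levels, and nowhere states that effectiveness may be declared from a secondary domain. This partly stands: the labels are there, and the remedy is to use them. But the hypothesis and objectives do not follow the labels, and the analysis section does not refer to them.

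A second reply also stands: the power figures depend on assumed effects. If readiness and DASS each had 99% power, independent joint power would be 0.8 × 0.99² = 78%, close to confidence alone. The 51% to 66% range shows what happens under equal power; it is not a forecast.

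A reader might infer that neither 80% power nor 5% error applies to the claim. The documents do not support that as a joint statement. Under all three required, error is controlled and power falls; under any one suffices, error rises and power does not fall. The word *and* in hypothesis 1 favours the first reading.

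**Conclusion.** The point holds as a missing decision rule. The plan attaches one effectiveness claim to three domains, sizes the study for one, tests all at 0.05 and does not say which pattern of results supports the claim.

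Depending on the rule adopted later, either the power or the error rate differs from what is stated, but not both under one simple rule. The size of the departure rests on the assumed 80% power per domain and correlations of 0 to 0.7; the 22.6% figure also needs the three DASS scales to be counted separately and the five tests to be independent. That the rule is missing depends on none of these assumptions. This should be corrected, because the plan as written lets a secondary result carry the main conclusion.

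**What to change.** In the general objective, the joint specific objective, hypothesis 1 and the Data Analysis section, state that effectiveness is judged on confidence alone. Name one directional contrast for that test in place of the overall ANOVA test, which has no direction. Baseline to 1 month as a house officer is a natural choice, being the only contrast measured for all three outcomes.

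Then choose one of two treatments for the rest:

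1. Report readiness and DASS as supportive, with confidence intervals and no effectiveness claim.
2. Test them at 0.05 in fixed order, readiness and then DASS, each only if the previous step is significant in the favourable direction. The DASS step needs a stated rule for its three scales, such as Holm.

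Either treatment is a short text change and leaves 208 as it is. The downside is that no confirmatory claim can be made for readiness or DASS if confidence fails. Keeping a three-domain claim instead would require sizing for it, about 309 enrolled under the assumptions shown. None of this addresses the absence of a control group, which limits what any pre-post change can show.

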#### LITERATURE REVIEW

#### Current Housemanship (HO) Scenario Worldwide and in Malaysia

Reduced psychological well-being amongst House Officers (HOs) is a known worldwide issue. For example in Norway, 11% of house officers are reported to have mental health problems needing treatment. (Tyssen, Vaglum, Gronvold, & Ekeberg, 2000). In the UK (Midlands), 46% is said to have clinical depression (J Firth-Cozens, 1990). The numbers don't run far amongst local Malaysian studies where it is said to be at a range of around 31-58% reported on various psychological conditions.

For example 31% of HOs are reported to be distressed, 36.6% indicates a high level of emotional burn out and the level of stress to be 34% in Kuala Lumpur and as high as 58% in Kota Kinabalu. (Al-Dubai et al., 2013; Shahruddin et al., 2016; Yusoff et al., 2011)

There many consequences of this psychological impact towards the HOs themselves, the healthcare system and towards the nation as a whole. Among the direct impact of stressed HOs is the number of them completing training within the allocate two years has been decreasing from 86.4% in 2009 to only 58.8% in 2012.(Lim, 2017) The dropout rate, which is defined as HOs not completing their training within 5 years is said to be slowly increasing from 3.7-4.8% per batch year.

A high level of stress is related is likely to affect thoughts of quitting HOship by up to three times, as evidenced in 2016 where 1.2% of HOs were either terminated or quit due to the inability to cope with stress. (Lim, 2017; Shahruddin et al., 2016)

#### **Causes of Stress amongst HOs**

Many studies have linked the causes of HO stress to be related with performance issues. This can be related to dealing with patient demands, intensity of the workload, mental strain and feeling

overworked (J Firth-Cozens, 1990; Tyssen et al., 2000; Williams, Dale, Glucksman, & Wellesley, 1997; Yusoff et al., 2011).

One of the contributing factors that cause this burden is the lack of confidence in performing. This has been described by participants of these studies to be "coping with diagnostic uncertainty", "perceived lack of skills", 'fear of making mistakes', and feeling "insecure". (Al-Dubai et al., 2013; Tyssen et al., 2000; Williams et al., 1997; Yusoff et al., 2011)

A qualitative study done amongst nursing students with regards to their clinical practice highlighted the feeling of anxiety as a result of feeling incompetent and lack of skills and knowledge (Sharif & Masoumi, 2012). Another study done on Senior House Officers in the UK also derived that confidence levels are linked to psychological distress (Williams, Dale, Glucksman, & Wellesley, 1997). Although these two studies were not done among House Officers specifically, it highlights the psychological impact of lack of confidence, skills and knowledge in the clinical setting.

Other factors said to be a contributor to this issue is poor social life and work balance including time management, interpersonal skills, and factors related to financial issues. (Al-Dubai et al., 2013; Yusoff et al., 2011)

#### **Impact of Stressed HOs**

Apart from the impact of prolonged and termination of training as mentioned earlier, there is a huge economic implication related to stressed HOs. As we know, training of doctors cost around RM500, 000 or even more per person. Hence this leaves a huge economic burden to our nation. (afterschool.my, 2016; The Straits Times, 2017)

Apart from that, stressed HOs can lead to substandard quality of care and patient safety issues as high levels of stress and depression is associated with lower standard of care. (J Firth-Cozens, 1990; Jenny Firth-Cozens & Greenhalgh, 1997)

#### The Housemanship (HO) Preparatory Module for Medical Graduates

Currently, there are HO Preparatory courses offered by independent bodies to address the above mentioned issues.(The Star, 2017) Medicorp offers regular training 10 times per year with 50-100 participants each course for the past 3 years.

Medicorp takes into account that peer training is one of the top learning methods preferred by junior doctors, apart from textbook and online materials (Wiggins et al., 2013). Hence, this training course relies heavily on volunteers mainly feedback from participants and its alumni. To date there has been more than 20 courses with more than 1500 participants who have benefited from this course. The courses are now run in 3 different states based on demand, Selangor, Sabah and Kelantan. They are followed up even after the course via social media networks and whatsapp groups for further support.

Preparatory housemanship training is very scarce here in Malaysia, especially those that are aimed at helping housemen be more functioning, motivated and be familiar with the system. Research done on these training modules are also very limited if not done at all.

We aim to evaluate this peer-lead course to see its effect on medical graduates 'confidence, *readiness*, and psychological wellbeing to better prepare them for housemanship training.

With the improvement of these factors it is hoped that this will reduce the level of stress amongst the junior doctors just starting work to give them a head start to become a more motivated doctor. The results of this course will further help to refine this module to be a more comprehensive and effective module and create an assessment tool for future training modules.

